and the low electronic noise of the system. (The technology provides better resolution than alternate cytometry technologies, like mass cytometry (CyTOF), with higher throughput, less cell loss, and a more robust hardware platform.) [name] developed a number of antibody staining panels for the system, including a panel that assesses many immune checkpoint molecules at once, and a pan-cytokine/global T-cell activation panel. Table 1 lists the markers studied with each panel. There are three notable advantages of highly multiplexed flow cytometry panels like these. First, they allow broad screening of many markers in order to find the most sensitive biomarkers in a particular disease setting. Second, by finely and precisely characterizing combined expression of every marker studied at the single cell level, a more detailed, mechanistic understanding of responses is possible than with serum, secretion, or bulk population assays. Finally, the technology is sample sparing; it provides maximal information (about protein expression) from a single vial of cells; this will be important given the relatively low numbers of cells collected from BAL. Though a number of institutions now have high-parameter flow cytometry technology, these panels have not been successfully developed elsewhere, and those institutions do not have [name] expertise in application of this technology.

Although this approach is novel in immuno-oncology, there is precedent, particularly from studies of vaccine responses. In healthy individuals, baseline peripheral blood CD8⁺ T cell HLA-DR⁺CD38⁺ and Ki67⁺Bcl-2^{low} expression is 0.5-2% and less than 0.5%, respectively (26). After immunization of healthy volunteers with the smallpox vaccine, up to 40% of peripheral blood CD8⁺ T

cells displayed HLA-DR⁺CD38⁺Ki67⁺Bcl-2^{low} (26). Similarly, in 29 patients with advanced NSCLC started on PD-1/PDL-1 axis inhibitory antibodies, approximately 70% of patients had a 1.5-fold increase in peripheral blood Ki67⁺CD8⁺ T cells demonstrating high levels of expression of DR⁺CD38⁺ Bcl-2^{low} and PD-1 post-treatment (27). Approximately 25-80% of these responding Ki67⁺CD8⁺PD-1⁺T cells expressed intra-cellular granzyme B, consistent with cytotoxic potential (27). Epstein-Barr Virus (EBV) -specific CD8⁺T cells had minimal activation and proliferation after PD-1 targeted therapy suggesting these CD8⁺

CONFIDENTIAL

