T cell responses may be tumor specific (27). Importantly, 80% of patients who developed these CD8⁺ T cell responses within 4 weeks of starting anti-PD-1 therapy had a clinical benefit.

In addition to assessing for pan-cytokine/global T cell activation and expression of immune checkpoint molecules in peripheral blood mononuclear cells utilizing flow cytometry technology, the NanoString[™] can assess for a variety of other immune biomarkers from peripheral blood. The NanoString[™] platform offers the convenience of straightforward high-throughput mRNA quantitation using RNA barcodes to probe and count mRNA transcripts of interest (28). The pre-designed OncoImmune[™] Profile panel, which measures 770 gene targets most relevant in tumor immunobiology.

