4.2.3 Sub-Set Analysis and Exploratory Endpoints

- Investigation of changes in peripheral blood CD8⁺ T cells displaying a combination of Ki67⁺, PD-1+, HLA-DR⁺, CD38⁺, and Bcl-2^{low} after BCI at each dose level. This sub-set analysis will investigate if there is an optimal freeze time duration for inducing anti-tumor immune responses.
- 2) Investigation of changes in peripheral blood CD8⁺ T cells displaying a combination of Ki67⁺,PD-1+, HLA-DR⁺, CD38⁺, and Bcl-2^{low} after BCI at each dose level. This sub-set analysis will investigate if the combination of cryoablation and current active cancer treatment will lead to enhanced increases in percent of peripheral blood CD8⁺ T cell expression of PD-1 and Ki67 and/or CD8⁺ T cells displaying an activated effector-like phenotype.

5 Study Enrollment and Withdrawal

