6.1 Description of BCI

6.1.1 Administration of BCI

This will be an open label, phase I pilot study without a control group. As described in Section 2.2, the Flexible ERBECRYO[™] Probe of 1.9mm outer diameter (ERBE, Inc., Tubingen, Germany) will be advanced through a bronchoscope to reach the target peripheral tumor, alternatively the ERBECRYO[™] 2 single-use flexible 1.1mm outer diameter cryoprobe will be used if robotic bronchoscopy is being performed. The flexible cryoprobe, which reaches a minimum reported temperature of -89°C, will be applied to the target tumor. Freeze time will be administered based on a dose escalation protocol, as described below. The freeze phase will be followed by a passive thaw phase, which will occur until the flexible cryoprobe has separated from the target tissue. The total number of freeze-thaw cycles will be performed (depending on tumor size) from distal to proximal within the target tumor. For each one centimeter of the longest diameter, one freeze-thaw cycle will be performed. The flexible cryoprobe will only be inserted into one airway to facilitate the cryoablation. Providers will be instructed to remain greater than 2 cm away from critical structures. The objective will not be to completely engulf the peripheral tumor in an ice ball, but to cryoablate a portion of the peripheral tumor.

We will evaluate for formation of an "ice ball" with fluoroscopy as well as via bronchoscopic visualization (when feasible) as we perform BCI. We will note the presence or absence of discernible ice ball formation for each patient at each dose level after completion of the BCI procedure.

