10.4.7 Additional Sub-Group Analyses

Sub-group analyses as described below will employ Wilcoxon signed-rank tests as described above for secondary analyses. In particular:

- 1) We will compare changes in pre- and post BCI peripheral blood CD8⁺ T cells expressing a combination of Ki67⁺,PD-1+, HLA-DR⁺, CD38⁺, and Bcl-2^{low} at each dose level.
- 2) In the subset of participants receiving active treatment (radiation therapy, chemotherapy, and/or immunotherapy in the past 30 days) for non-small cell lung cancer, we will investigate if the combination of cryoablation and his/her current treatment will lead to enhanced increases in the percent of CD8⁺ T cells expressing a combination of Ki67⁺,PD-1+, HLA-DR⁺, CD38⁺, and Bcl-2^{low} compared to participants treated with BCI alone.

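### With no therapy-only group, the active-treatment subgroup comparison cannot show that BCI combined with current therapy enhances the CD8+ response

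*Combined protocol and SAP*

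**What the plan says.** Section 4.2.3, item 2, says the sub-set analysis "will investigate if the combination of cryoablation and current active cancer treatment will lead to enhanced increases" in the CD8+ phenotype. Section 10.4.7, item 2, repeats the aim: "we will investigate if the combination of cryoablation and his/her current treatment will lead to enhanced increases". It defines the subset as participants who had radiation, chemotherapy and/or immunotherapy in the 30 days before, and sets the comparator: "compared to participants treated with BCI alone". The test is given at the head of that section: "Sub-group analyses as described below will employ Wilcoxon signed-rank tests as described above for secondary analyses".

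On design, section 6.1.1 states: "This will be an open label, phase I pilot study without a control group". Section 5.1 permits concomitant chemotherapy, immunotherapy and radiation; none of it is assigned by the study.

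On what therapy alone does to the marker, section 2.1 (VI) cites 29 patients with advanced NSCLC who started PD-1/PD-L1 antibodies, of whom "approximately 70% of patients had a 1.5-fold increase in peripheral blood" Ki67+ CD8+ T cells of the relevant phenotype. It adds that 80% of those who developed these CD8+ "T cell responses within 4 weeks of starting anti-PD-1 therapy had a clinical benefit".

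**The concern.** The wording asks whether the combination produces the larger rise. To answer that, one must know what the therapy would have done over the same days without BCI. The plan has no such group, so a larger rise in treated participants could be the therapy's own effect, synergy, or a difference between the kinds of patient in the two groups.

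Sections 2.2.4 and 10.5 say the results should inform later studies of BCI with anti-PD-1 therapy. A difference read as enhancement would lend those studies support that the data cannot give. The error can also run the other way. If therapy had already raised the day-0 value and the marker then fell back, real synergy could be hidden.

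**Working it through.** **Plan's own figure.** None is given for this comparison. The only power statement (section 10.5: 15 subjects, 0.75 SD, correlation 0.5, about 80%) concerns the overall pre/post change. With SD of change = SD × √(2 × (1 − 0.5)) = 1 SD, it reproduces approximately: 82.8% by the normal approximation and 77.1% by a paired t-test.

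**What the comparison estimates.** Let b be the BCI effect on the pre-to-post change, t the therapy's own effect from day 0 to the post-BCI sample, s the synergy and d the selection difference between groups.

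- BCI plus therapy: b + t + s + d
- BCI alone: b
- Difference: t + s + d

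Isolating s needs an estimate of t, hence therapy without BCI, and also control of d. Neither is planned.

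**The named test.** A signed-rank test is paired within participants and cannot compare different participants. Run inside the treated subset, it tests b + t + s + d = 0. With d = 0, 8 participants and normal changes of SD 1, it rejects about 40% of the time if only BCI acts (0.75 SD) and about 40% if only therapy acts (0.75 SD). A two-sample test would compare the right people but still estimates t + s + d.

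**How large the problem could be.** Set b = s = d = 0. From the protocol: 70% of checkpoint-inhibitor starters exceed a 1.5-fold rise, alpha is 0.05, and total enrolment is 15 to 24. Assumed, because the documents do not say: group split, SD of the log fold-change (0.5 or 0.8), share of recent starters, a two-sided rank-sum test, and no effect of other therapies on the marker.

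Mean log rise in starters: ln(1.5) + 0.524 × SD, which is 0.405 + 0.262 = 0.667 for SD 0.5 and 0.405 + 0.419 = 0.825 for SD 0.8 (rounded).

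Two timings were used:

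- *Upper bound:* the whole rise falls after day 0.
- *Spread:* therapy started u days before day 0, with u uniform over 0 to 30, a linear rise over 28 days, and the sample taken at day 14. The share of the rise falling after day 0 is 14/28 = 0.5 for u below 14, averages 0.25 for u from 14 to 28, and is 0 beyond. The mean is (14 × 0.5 + 14 × 0.25)/30 = 0.35.

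False enhancement (treated group significantly higher), 8 treated vs 16 BCI alone, 20,000 simulated trials per cell, SD 0.5 / 0.8:

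| Share of treated who are recent starters | Upper bound | Spread |
|---|---|---|
| All | 80% / 58% | 16% / 11% |
| Half | 24% / 17% | 6.7% / 5.4% |
| A quarter | 9% / 7% | 4.2% / 3.5% |
| None | 2.2% / 2.2% | 2.2% / 2.2% |

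The nominal rate in this direction is 2.5%. With all treated participants recent starters, 12 vs 12 gives 85% / 64% (upper bound) and 17% / 12% (spread); 6 vs 9 gives 62% / 42% and 12% / 9%.

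**The case against.** The strongest reply is that the pre-BCI sample already removes much of the therapy effect. The cited rise is counted from the start of therapy. For someone who started before day 0, part or all of it is in the baseline and is subtracted. This stands, and it is why the upper-bound column should not be taken as an estimate. A reader might infer that the analysis would falsely show enhancement in most trials. The documents do not support that: the subset is defined by receiving therapy in the past 30 days, not by starting it, it includes chemotherapy and radiation, and no therapy-alone effect on this marker is reported for either.

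Second, the text does not use the words interaction or synergy, and a larger rise than with BCI alone can be described. This stands in part. The description is legitimate, but attributing the rise to the combination is not.

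Third, the analysis is exploratory, section 10.4.1 says the study is not powered for secondary outcomes, and no dose or safety decision uses this subgroup. This stands and lowers the severity. It does not repair the comparison, because lack of power is imprecision, whereas here the quantity estimated is not the one named.

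The virus-specific control in section 4.2.2 does not help. Section 2.1 (VI) says EBV-specific cells were minimally activated after PD-1 therapy, so the control cannot tell a checkpoint-inhibitor effect from a BCI effect.

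**Conclusion.** The point holds as a limit on interpretation. The comparison estimates therapy effect plus synergy plus selection, so neither a difference nor its absence can be attributed to the combination. That conclusion needs no simulation.

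The size of the inflation is unknown. At 8 vs 16 it ranges from about 3.5% to 7% (a quarter to a half recent starters, spread timing), through 11% to 16% (all recent starters, spread timing), to an upper bound of 58% to 80%. All of these rest on the assumed split, SDs, timing and rank-sum test.

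A reader might also infer that participants more than 30 days from the start of therapy give a clean comparison, because the cited responses arose within 4 weeks. Section 2.1 does not say the response ends then, and that comparison would be just as unrandomised. Severity is minor.

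**What to change.** In 4.2.3 item 2 and 10.4.7 item 2, replace the aim of showing enhanced increases with a descriptive one: summarise the pre-to-post change in the CD8+ marker by treatment status at day 0. Add a sentence saying that, because there is no therapy-only group and therapy is not randomised, a difference between the groups, or its absence, is not evidence for or against enhancement by the combination.

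Optionally, list for each participant the type of therapy and the time since the current regimen began. Treatment history is already collected (sections 7.1.2 and 7.3.4), but start dates are not named there and would have to be recorded. Do not make participants more than 30 days from start the main comparison: the groups would be very small and the same confounding would remain.

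The main change needs no extra patients, samples or visits. Its cost is a weaker claim about the combination.

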10.4.8 Tabulation of Individual Response Data

Individual participant data will be listed by time points of peripheral blood collection day.

10.5 Sample Size

We will aim to enroll approximately 24 patients. The exact number will be determined based on our dose escalation protocol (as described in section 6.1.2).

The table below gives the operating characteristics of this design, presenting the likelihood of escalation when the true DLT rate takes various values. For example, if the true DLT rate is 60%, the probability of escalation is only 0.08. If the true DLT rate is 10%, the probability of escalation is 0.91.

| True DLT Rate | 10% | 20% | 30% | 40% | 50% | 60% | 70% | 80% | 90% |
|---------------------------|------|------|------|------|------|------|------|--------|--------|
| Probability of Escalation | 0.91 | 0.71 | 0.49 | 0.31 | 0.17 | 0.08 | 0.03 | <0.001 | <0.001 |

The small sample size will not provide sufficient power to definitively address the secondary endpoint of measuring BCI induced anti-tumor immune responses. For example, 15 subjects provide approximately 80% power to detect a difference of about 0.75 standard deviations between pre- and post-BCI peripheral blood CD8⁺ T cell expression of PD-1 and Ki67, conservatively assuming a within-subject correlation between assessments of 0.5. However, our results will be critical for informing the design of further studies aimed at estimating response and survival rates with BCI combined with anti-PD1- therapy for the treatment of advanced non-small cell lung cancer.

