6.1.2 Dose Escalation Protocol

A standard 3+3 dose escalation strategy will be used. The table below shows the doses that will be provided. Three participants will be initially enrolled at Level 1. If none of the first three participants at a given dose experiences dose-limiting toxicity (DLT), the dose will be escalated. If two or more of the first three participants experience DLT, the prior dose will be deemed the maximum tolerated dose (MTD) and the study will be terminated. If one of the first three participants experiences DLT, an additional three participants will be enrolled at the same dose. If among these six, only one experiences DLT, the dose will be terminated. If two or more of six experience DLT, the prior dose will be deemed the MTD and the study will be terminated. If the MTD is reached and only three participants have been treated at that dose, an additional three will be treated to ensure six subjects are treated at the MTD. DLT are defined in Section 4.1.1 (Primary Study Endpoints: Feasibility and Safety).

| Dose Level | Freeze Time (per site) | Thaw Time |
|------------|------------------------|---|
| Level 1 | 1 second | Will last until the probe separates from target tissue* |
| Level 2 | 2 seconds | Will last until the probe separates from target tissue* |
| Level 3 | 3 seconds | Will last until the probe separates from target tissue* |
| Level 4 | 5 seconds | Will last until the probe separates from target tissue* |
| Level 5 | 10 seconds | Will last until the probe separates from target tissue* |
| Level 6 | 20 seconds | Will last until the probe separates from target tissue* |

CONFIDENTIAL

| Level 7 | 30 seconds | Will last until the probe separates from target |
|---------|------------|---|
| | | tissue* |

6.1.3 **Procedures for Training of Clinicians on Procedural Intervention**

The NYU Interventional Pulmonary service has extensive experience using the flexible cryoprobe for debulking of central airway tumors. BCI will be performed by a board-certified, NYU Interventional Pulmonologist.

Only patients with the presence of a bronchus or airway path leading directly to the peripheral lung tumor will be eligible to undergo BCI. The peripheral tumor will also need to be identified by radial EBUS prior to performing BCI. If the peripheral tumor is unable to be identified by radial ultrasound within 20 minutes, then the patient will not be a candidate to undergo BCI.

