10.2 Statistical Hypotheses

- 1) BCI will be feasible and safe, with a maximum tolerated dose to be determined in this trial.
- 2) Post-BCI peripheral blood will demonstrate an increase in the percent of CD8⁺ T cells expressing a combination of Ki67⁺, PD-1+, HLA-DR⁺, CD38⁺, and Bcl-2^{low} compared to pre-BCI peripheral blood CD8⁺ T cells.
- 3) CD8+ T cell responses to BCI will be greater among subjects with high PD-1 expressing T cells in BAL effluent.

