10.4 Description of Statistical Methods

10.4.1 General Approach

- Continuous data will be summarized with means and standard deviations.
- Categorical data will be summarized with frequencies and percentages.
- *P* values will be considered statistically significant at the 0.05 level. Note that the study is designed to determine the MTD, and thus is not powered to detect statistically significant differences in any of the secondary outcomes.

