10.4.4 Analysis of the Secondary Endpoint(s)

Wilcoxon signed-rank tests will be used to assess paired pre- and post-BCI peripheral blood measurements, and to assess paired post-BCI peripheral blood CD8⁺ T cell responses and T cell PD-1 expression in BAL effluent.

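### The Section 10.5 table prints an escalation probability of <0.001 at an 80% true DLT rate; the 3+3 rule behind the rest of the table gives 0.009

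*Combined protocol and SAP*

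**What the plan says.** Section 10.5 (Sample Size) presents the operating characteristics of the 3+3 design as one probability of escalation for each true DLT rate. The columns from 10% to 70% run 0.91, 0.71, 0.49, 0.31, 0.17, 0.08, 0.03. The 70%, 80% and 90% columns read "0.03 | <0.001 | <0.001".

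The rule itself is in Section 6.1.2: "If none of the first three participants at a given dose experiences dose-limiting toxicity (DLT), the dose will be escalated". One DLT in the first three leads to three more participants at the same level. Two or more DLTs end escalation.

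Section 10.5 also gives a power figure for the immune endpoint: "15 subjects provide approximately 80% power to detect a difference of about 0.75 standard deviations", "conservatively assuming a within-subject correlation between assessments of 0.5". It offers this as an illustration of why the sample cannot settle the secondary endpoint. Section 10.4.1 adds that the study "is not powered to detect statistically significant differences in any of the secondary outcomes". The planned test is in Section 10.4.4: "Wilcoxon signed-rank tests will be used to assess paired pre- and post-BCI peripheral blood measurements".

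**The concern.** The table is the plan's only numerical statement of how its primary, MTD-finding design behaves, and the study is first-in-human. A reader uses the right-hand columns to judge how well the rule protects against passing a very toxic level. An entry that is too low there errs in the reassuring direction.

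The drop from 0.03 at 70% to less than 0.001 at 80% is also too steep on its face. The chance of no DLT in three participants falls only from 0.027 to 0.008 between those two rates.

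The power sentence raises a lesser question. It names neither a method nor a sidedness, so a reader who checks it with a small-sample calculation for the planned test may not get 80%.

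**Working it through.** **Escalation table**

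Inputs: the rule in Section 6.1.2, with p the true DLT rate, and the printed values in Section 10.5. Escalation follows either 0 of 3 DLTs, or 1 of 3 and then 0 of the next 3:

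P(escalate) = (1-p)^3 + 3p(1-p)^2 × (1-p)^3 = (1-p)^3 + 3p(1-p)^5

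| True DLT rate | Printed | 0 of 3 | 1 of 3, then 0 of 3 | Sum |
|---|---|---|---|---|
| 10% | 0.91 | 0.729 | 0.1771 | 0.906 |
| 20% | 0.71 | 0.512 | 0.1966 | 0.709 |
| 30% | 0.49 | 0.343 | 0.1513 | 0.494 |
| 40% | 0.31 | 0.216 | 0.0933 | 0.309 |
| 50% | 0.17 | 0.125 | 0.0469 | 0.172 |
| 60% | 0.08 | 0.064 | 0.0184 | 0.082 |
| 70% | 0.03 | 0.027 | 0.0051 | 0.032 |
| 80% | <0.001 | 0.008 | 0.00077 | 0.0088 |
| 90% | <0.001 | 0.001 | 0.00003 | 0.00103 |

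The formula matches the seven columns from 10% to 70%, so the method behind the table is not in doubt.

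- At 80%: 0.2^3 + 3 × 0.8 × 0.2^5 = 0.008 + 0.000768 = 0.00877. Against the bound of 0.001 that is a factor of about 8.8, or a difference of 0.0078.
- At 90%: 0.1^3 + 3 × 0.9 × 0.1^5 = 0.001 + 0.000027 = 0.00103.

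One assumption needs stating. The formula escalates after 1 DLT among 6, whereas Section 6.1.2 says that in this case the dose is terminated. If that route is removed, the 0-of-3 column applies alone. The 80% entry is then 0.008, still eight times the printed bound, and the 90% entry is exactly 0.001.

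**Power statement (secondary)**

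Inputs: 15 pairs, a difference of 0.75 SD and correlation 0.5 (Section 10.5); "values will be considered statistically significant at the 0.05 level" (Section 10.4.1). At correlation 0.5 the SD of the paired difference is SD × sqrt(2 × (1 - 0.5)) = SD, so the standardised effect stays at 0.75. The plan does not state sidedness. Two-sided is assumed below, with one-sided shown as a variant.

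- Normal approximation with the Wilcoxon asymptotic efficiency 3/π: Φ(0.75 × sqrt(15 × 3/π) - 1.96) = Φ(0.88) = 0.81. Inverted for 80% power: n = (1.96 + 0.842)^2 / 0.75^2 × π/3 = 14.6, so 15. This reproduces the plan's figure.
- Normal approximation without the efficiency factor: 0.83.
- Paired t-test (noncentral t): 0.771; 16 pairs reach 0.80.
- Exact signed-rank test, by simulation (300,000 runs): 0.749 for normal differences, 0.779 logistic, 0.812 Laplace, 0.685 uniform.
- One-sided: 0.868 (paired t) and 0.848 (exact signed-rank, normal differences).
- Difference detectable with 80% power at 15 pairs, two-sided: 0.78 SD (paired t) or about 0.80 SD (exact signed-rank, normal differences).

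**The case against.** **On the table.** An 80% DLT rate is remote from the 5% to 12% pneumothorax and bleeding rates that Section 2.1 cites for transbronchial cryobiopsy. The absolute error is under 0.8 percentage points. The columns most likely to matter are right. Section 8.4 adds halting rules that the formula ignores and that could only make escalation rarer. Both entries would be true as <0.01, so a stray zero is a plausible cause, though this cannot be shown. All of this bears on the weight of the point, and it is why the point is minor. It does not rescue the 80% entry: the table describes the 3+3 rule alone, and the other columns follow that rule without the halting rules. The objection does succeed for the 90% entry, which is off only in the fifth decimal place and should not be put on a par with the 80% entry.

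**On power.** A reader might infer that the 80% is wrong and that 75% is the true value. The documents do not support that. The figure reproduces at 81% by a recognised formula suited to the planned test. The 75% depends on a two-sided test and normal differences, neither of which the plan states, and the hypothesis in Section 10.2 is directional: "Post-BCI peripheral blood will demonstrate an increase in the percent of". The sentence is hedged twice, and the plan disclaims power for secondary outcomes.

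A reader might also infer that the correlation of 0.5 is not conservative, or that fewer than 15 pairs will be available. Patients found not to have NSCLC do give no post-BCI blood (Section 7.1.2). But the plan contains no data pointing to a lower correlation. With about 24 patients targeted, 15 pairs already leave room for nine losses. Either inference would need an input that the documents do not provide.

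**Conclusion.** The 80% entry in the Section 10.5 table is wrong as printed: 0.0088 under the rule that generates the rest of the table, and 0.008 under the narrower reading of Section 6.1.2, against a stated bound of 0.001. The 90% entry, 0.00103, is marginally not below 0.001. The result rests only on independent DLTs with a common rate p and on the rule as described. It is a minor error in a stated property of the primary design. It does not show that the escalation rule is unsafe, because the rule itself is unaffected and a probability of 0.009 at that rate is still small.

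The power sentence is a hedged large-sample figure that could be refined. Under normal differences, correlation 0.5 and a two-sided 0.05 test, small-sample calculations fall 3 to 5 points below 80%.

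**What to change.** In the Section 10.5 table, replace the 80% entry with 0.009 and the 90% entry with 0.001, and state the formula and the assumption of escalation after 1 DLT among 6. Reconcile that assumption with the sentence in Section 6.1.2 under which the dose is terminated in that case. Which is intended is for the sponsor to settle. If 1 of 6 does not lead to escalation, the whole table needs recomputing from (1-p)^3: the 10% entry, for example, becomes 0.729, and the 80% entry 0.008.

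Optionally, reword the power sentence to say that 15 evaluable pairs give about 75-80% power for 0.75 SD at correlation 0.5, and name the test, the method of calculation, the sidedness and the assumed distribution of differences.

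The table correction and the power rewording are text changes only. They do not touch the sample size, the analysis or the conduct of the trial; the stated power becomes slightly less favourable.
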